8.3 Subject Withdrawal Criteria

Reasons for withdrawal may include, but are not limited to, the following:

- Either at investigator's request (e.g., non-ocular serious adverse event, subject non-compliance).
- Subject voluntarily withdraws consent.
- When the requirements of the protocol are not followed.
- When a subject is lost to follow-up. The investigator or his/her designee will try twice to reach the subject by telephone and will send a follow-up letter by certified mail before considering that the subject is lost to follow-up. These actions will be reported on the End of Study case report form (CRF) and a copy of the follow-up letter maintained in the investigator's file.

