8.3.3 Subject Completion

The subject has completed the study when they have completed Postoperative Visit 5. A subject who has missed visits or is missing study measurements will be continued in the study. Subjects who require further follow-up for an unresolved AE at the end of their study period will be followed according to [Section 12.4.4](#).

An exit CRF must be completed for all subjects who complete, prematurely discontinue, or are lost to follow-up from the clinical investigation.

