8.3.4 Subject Discontinuation

A subject MUST be discontinued **prior** to the final study visit for any of the following reasons:

- Change in eligibility prior to treatment

- Voluntary withdrawal
- Death
- Pregnancy
- Lost to follow-up
- Study terminated by Sponsor

Prior to discontinuing a subject, every effort should be made to contact the subject, schedule a final study visit, and obtain as much follow-up data as possible. Adverse events will be followed as described in **Section 12.4.4**. Subject withdrawals will be documented clearly on the source document and applicable CRF.

Notification of subject withdrawals will be made to the Sponsor or their designee through the IRT system and confirmed by the CRO.

Only subjects who are randomized but did not receive study treatment may be replaced. A new subject number will be assigned as long as the total number of treated subjects at the site does not exceed the maximum percentage of the total treated eyes in the study based on the number of active sites as outlined in **Section 7.2**. Subjects who are discontinued from the study following treatment will not be replaced.

Discontinued subjects should be followed outside of the study protocol according to the Investigator's normal standard of care.

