9.2 Postoperative Masked Examiners and Masked Roles

Each site should have at least two masked examiners to perform the post-operative measurements. It is preferred that the same masked examiner perform all post-operative measurements for an individual subject.

Subjects, masked examiners, the specular microscopy reading center employees, the Sponsor (other than the assigned unmasked contact) and the CRO, with the exception of the study monitors, will be masked to the OVD treatment received.

Masking of subjects during the surgical procedure (and during the course of the study) will be discussed during a site initiation visit by the Sponsor representative with the Principal Investigator and study staff. All surgical staff present during the cataract surgery (who are unmasked) will be instructed not to discuss the OVD treatment assignment in the presence of the subject. Intraoperative surgical staff present during the cataract surgery will further confirm their commitment to not disclosing the assigned OVD treatment assignment to a subject by signing a masking commitment form prior to the initiation of the cataract surgery. Documentation will be maintained in the site files.

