13.5.2 Primary Effectiveness Analysis

Specular microscopy of the central cornea will be completed preoperatively and at Visit 5 (90 ± 14 days postop). Images will be evaluated by a masked reading center. If multiple cell densities are obtained from the reading center for each eye visit, then the available counts will be averaged by eye and visit (Preoperative, Visit 5) to produce a single value for each eye visit.

If one or more ITT Population eyes has a missing mean ECD value either at the preoperative visit or at Visit 5 (including due to a missed visit or due to discontinuation), then the missing data will be imputed as follows. Prior to analysis, 25 imputations of missing mean densities will be produced using the Markov chain Monte Carlo method and the variables investigator, treatment, preoperative value, and postoperative value.

For each observation in the imputed datasets, the ECD loss in percent at Visit 5 will be calculated for each eye at each visit as follows:

$$\text{Loss (\%)} = \frac{\text{Preoperative Cell Density} - \text{Visit 5 Cell Density}}{\text{Preoperative Cell Density}} \times 100\%$$

The means and standard errors from the imputed datasets will be combined to produce a continuous variable summary of the ECD (cells / mm^2) at each visit (Preoperative, Visit 5) and the percent loss at Visit 5 by randomized treatment assignment for the ITT Population.

Loss (%) will be modeled as a function of the fixed class variables treatment and investigator, separately by imputation. The parameter estimates will be combined to produce a one-sided upper 95% confidence limit for the difference in percent loss between the test

and comparator OVDs and a p-value for the hypothesis test for the ITT Population. If the upper confidence limit is less than 5%, then the null hypothesis of inferiority will be rejected in favor of the alternative hypothesis of non-inferiority.

If there are no ITT Population eyes with missing ECD data, then imputation will not be performed. Instead, the available data will be analyzed and summarized as described above.

Sensitivity analyses of effectiveness will include a best-case analysis, a worst-case analysis, a tipping point analysis, and a complete case analysis (which will use only subjects who have cell density measurements at every scheduled visit), and analysis using the PP Set.

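### Section 8.3 lets a subject who has already received the OVD be withdrawn for non-compliance or a protocol departure, which can needlessly lose the only postoperative ECD value

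*Combined protocol and SAP*

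**What the plan says.** Section 8.3 opens with "Reasons for withdrawal may include, but are not limited to, the following". Its grounds include a request by the investigator, with a non-ocular SAE and subject non-compliance as examples, and "When the requirements of the protocol are not followed". No severity threshold is given, and neither ground is confined to the time before treatment. Section 9.4 defines a deviation as any failure to follow the protocol, so on a literal reading any deviation qualifies.

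Other sections point the other way:

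- Section 8.3.3: "A subject who has missed visits or is missing study measurements will be continued in the study".
- Section 11.1.3: all treated subjects are to be seen at five postoperative visits.
- Section 8.3.4: the list of mandatory discontinuations contains neither ground, and its eligibility item is limited in time: "Change in eligibility prior to treatment".
- Sections 9.3.2 and 9.3.4: use of an IOP-lowering agent in the circumstances described there does not lead to discontinuation; the subject is excluded from the Per Protocol and Best Case populations.
- Section 13.5.7: major deviations are handled by exclusion from the Per Protocol set.

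On what follows a discontinuation, 8.3.4 asks for every effort to hold a final visit and collect data. It then says "Discontinued subjects should be followed outside of the study protocol", and treated subjects are not replaced. Section 13.5.2 fixes the timing of the endpoint: "Specular microscopy of the central cornea will be completed preoperatively and at Visit 5". Missing ECD in the ITT population is imputed from investigator, treatment, preoperative value and postoperative value.

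**The concern.** In a trial with one intraoperative exposure, stopping treatment and stopping follow-up are separate matters, and after Day 0 only the second remains. Section 8.3 does not make the distinction. A departure that could simply be logged can end observation of an eye whose Day 90 ECD was obtainable.

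Two features make this more than a loss of precision. Surgical staff are unmasked (9.2) and the assigned OVD is handed to the investigator (Appendix C), so the person whose request can end follow-up generally knows the arm and how the surgery went. And the primary imputation fills in a withdrawn eye as typical of its arm, site and baseline density, whatever the reason it left. If eyes with a poor course were withdrawn more often from the test arm, the estimated difference in ECD loss would move toward non-inferiority.

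**Working it through.** **1. Compare the provisions by ground.**

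- *Missed visit or missing measurement, treated as non-compliance or a protocol departure:* 8.3 permits withdrawal; 8.3.3 says the subject continues. This is a direct conflict.
- *Any other departure, or a non-ocular SAE, after treatment:* 8.3 permits withdrawal; 8.3.3 is silent; 11.1.3 says all treated subjects are seen five times. The conflict is with 11.1.3 only.
- *IOP-lowering treatment as described in 9.3.2 and 9.3.4:* explicitly not a reason to discontinue. Here the protocol already separates non-adherence from follow-up, and 8.3 does not follow that pattern.

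**2. Can the exit visit supply the endpoint?** The Visit 5 window is 90 ± 14 days, so it opens on Day 76. Section 8.3.4 ties the final visit neither to Day 90 nor to specular microscopy, and Appendix A schedules postoperative ECD at Visit 5 alone.

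**3. Reproduce the plan's figure.** Inputs from 13.3.2: SD 14.2, 165 per arm, margin 5, true difference 0, one-sided 0.05.

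- SE = 14.2 × √(2/165) = 1.563 points.
- The two-sample t-test (noncentral t) gives 93.90% power, as stated.
- With all 184 per arm observed, power is 95.8%. The planned 10% loss therefore costs about 2 points of power, and the issue is bias.

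**4. Stress test.** Assumptions not in the documents: a fraction w of the test arm only is withdrawn, and those eyes lose D points more than the imputed value.

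Shift toward non-inferiority = w × D.

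Type I error at a true difference of 5 = Φ(w × D / 1.563 − 1.645).

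| w | D | Shift | Type I error |
|---|---|---|---|
| 1% | 10 | 0.1 | 5.7% |
| 3% | 10 | 0.3 | 7.3% |
| 5% | 10 | 0.5 | 9.3% |
| 1% | 20 | 0.2 | 6.5% |
| 3% | 20 | 0.6 | 10.4% |
| 5% | 20 | 1.0 | 15.7% |

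Five percent of 165 is about 8 eyes. Repeating the 5% rows with 184 × 0.95 observed eyes per arm gives 9.4% and 16.2%, so the choice of base matters little.

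**5. Both arms.** The general shift is w(test) × D(test) − w(control) × D(control). With equal values in the two arms it is zero.

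**The case against.** A reader might infer that 8.3 contradicts 8.3.3 on every ground. It does not: 8.3.3 covers only missed visits and missing measurements. Nor is it a contradiction that the permissive list in 8.3 is longer than the mandatory list in 8.3.4.

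A reader might also infer that informative missing ECD will result, or that an investigator could choose eyes by their ECD. The documents support neither. Withdrawal is optional, and no expected number is given. Postoperative ECD does not exist before Visit 5 and is then read by a masked center, so selection could act only through proxies such as the surgical course. The SAE example is non-ocular, and the protocol-departure ground does not say who decides. Withdrawals are notified through the IRT and confirmed by the CRO (8.3.4), and reasons are tabulated (13.5.5).

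The plan also has worst-case and tipping-point analyses for ECD (13.5.2), which address this kind of missingness. Section 11.1.4 puts a visit meant to satisfy a scheduled visit on that visit's form even when it is out of window, so an early exit visit might be recorded as Visit 5.

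These points limit the claim but do not remove it. The sensitivity analyses test the assumption without recovering the value, and the non-inferiority decision rests on the primary analysis. Section 11.1.4 does not say that an exit visit qualifies, and an early ECD would not be a Day 90 ECD. The stress test is one-directional by construction, and a 20-point excess is 20/14.2 = 1.4 planning SDs for every withdrawn eye.

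**Conclusion.** The point holds as a risk that the plan creates and could avoid. As written, 8.3 permits obtainable primary-endpoint data to be lost for treated eyes that stay in ITT, and it is inconsistent with 8.3.3 (missed visits and measurements) and with 11.1.3 (all treated subjects).

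The range of 5.7% to 15.7% for type I error is a one-arm stress test, not an estimate. It rests on the assumed withdrawal fraction, the assumed excess loss and the absence of offsetting withdrawals in the control arm. The sponsor should correct the text. The plan's own sample size and power figures are not in dispute.

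**What to change.** State in 8.3 and 8.3.4 that, after OVD exposure, non-compliance or a protocol departure is recorded as a deviation, is handled through the Per Protocol definition in 13.5.7, and is not by itself a reason to end follow-up. Add that any treated subject discontinued for a reason other than withdrawal of consent, death or loss to follow-up is still asked to attend the remaining scheduled visits, including ECD at Visit 5. The sentence in 8.3.4 that sends discontinued subjects outside the protocol must then be aligned.

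The same revision has to reconcile 8.3, 8.3.3, 8.3.4 and 11.1.3 with the other discontinuation provisions: use of another OVD (9.1.3), pregnancy (8.3.4, 12.4.6), withdrawal after an SAE (8.3), and termination by the sponsor (8.3.4, 11.3.1). Which of these should end participation is a clinical and sponsor decision that this review does not prescribe. What is needed is that the sections agree and say whether Visit 5 ECD is still sought.

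The cost is coordinated wording across these sections and a few more completed visits that are already on the schedule.

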8.3.1 Subject Enrollment

The subject is considered enrolled in the study at the time the IRB/EC approved ICF is signed.

8.3.2 Subject Screen Failures

A subject who fails to meet eligibility criteria is considered a screen fail. Subjects who screen fail will not be eligible for rescreening.

8.3.3 Subject Completion

The subject has completed the study when they have completed Postoperative Visit 5. A subject who has missed visits or is missing study measurements will be continued in the study. Subjects who require further follow-up for an unresolved AE at the end of their study period will be followed according to [Section 12.4.4](#).

An exit CRF must be completed for all subjects who complete, prematurely discontinue, or are lost to follow-up from the clinical investigation.

8.3.4 Subject Discontinuation

A subject MUST be discontinued **prior** to the final study visit for any of the following reasons:

- Change in eligibility prior to treatment

- Voluntary withdrawal
- Death
- Pregnancy
- Lost to follow-up
- Study terminated by Sponsor

Prior to discontinuing a subject, every effort should be made to contact the subject, schedule a final study visit, and obtain as much follow-up data as possible. Adverse events will be followed as described in **Section 12.4.4**. Subject withdrawals will be documented clearly on the source document and applicable CRF.

Notification of subject withdrawals will be made to the Sponsor or their designee through the IRT system and confirmed by the CRO.

Only subjects who are randomized but did not receive study treatment may be replaced. A new subject number will be assigned as long as the total number of treated subjects at the site does not exceed the maximum percentage of the total treated eyes in the study based on the number of active sites as outlined in **Section 7.2**. Subjects who are discontinued from the study following treatment will not be replaced.

Discontinued subjects should be followed outside of the study protocol according to the Investigator's normal standard of care.

8.3.5 Subjects Lost to Follow- up

Subjects who do not return for scheduled Postoperative Visit(s) as defined by the visit window, and cannot be contacted, may be considered lost to follow-up. All follow-up attempts will be documented and kept with the subject's source documentation, and the applicable CRFs will be completed.

Efforts shall be made to keep the number of subjects lost to follow-up to below 10% of the number of subjects treated.

9 Treatment Plan

9.1 Methods of Assigning Subjects to Treatment Groups

Up to approximately 368 subjects (368 eyes) will be randomized in a 1:1 ratio to receive DVisc40 (test) OVD or VISCOAT® (control) OVD during surgery.

9.1.1 Treatment Allocation

At the time of surgery, subjects will be randomly assigned to either the DVisc40 OVD group (test) or the VISCOAT® OVD group (control) based upon a predetermined randomization scheme. Randomization will be on a 1:1 schema.

9.1.2 Randomization Method

Subjects will be randomly assigned to one of the two OVD materials according to the randomization scheme to be provided in a computer-generated randomization code by a biostatistician otherwise not involved with the study.

Interactive Response Technology (IRT) will be utilized for randomization in this study. Randomization will be stratified by site, age group and cataract severity. A method other than stratification may be employed to balance randomization. If so, the method will be specified in the SAP. The randomization codes will be established in blocks such that approximately the same number of subjects will be assigned to the DVisc40 OVD or VISCOAT® OVD treatment groups at each site.

Subjects will be randomized to 1 of 2 treatment groups in a ratio of 1:1 (DVisc40:VISCOAT®). Each screened subject will be assigned a unique 5-digit subject number assigned by the site accessing the IRT system. The subject number assigned by the IRT system will consist of the 2-digit investigational center/site number (pre-assigned by Sponsor or its designee) and the 3-digit chronological screening order number starting with 001 (e.g. 01-001, 01-002). The study device kit will be assigned to subjects based on a randomization code and the kit will be dispensed to the subjects at Day 0 (Operative Visit) by the IRT system. The assigned kit number should be recorded in the subject's source documents and applicable case report form. A study device log will document the inventory and dispensing of study device at each investigational center.

9.1.3 Treatment Replacement

No other OVD can be used intraoperatively in conjunction with either the test or control OVD. Use of any other OVD will require immediate discontinuation of a subject from the study. If the surgeon feels more than one vial of test or control OVD is required to complete the surgery, this will be allowed and the incidence of such events will be reported.

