9.3.2 Intraoperative Medications

The Investigator will use their standard surgical medications. A complete list of the standard regimen of intraoperative surgical medications used will be provided to the Sponsor or its designee prior to initiation of the study. Absolutely no IOP-lowering medications may be used prophylactically. If an IOP-lowering medication is used intraoperatively (e.g., in the case of surgical complication), the medication must be recorded in the subject's source documents and on the applicable case report form(s). Use of an IOP lowering agent under these conditions is not a reason for discontinuing a subject from the study. However, such subjects are to be excluded from the Per-Protocol (PP) and Best Case analysis populations.

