9.3.4 Management of Raised IOP

Treatment for IOP < 30 mmHg should be avoided if possible unless the Investigator considers it necessary for the safety and well-being of the subject. In the case of treatment of IOP < 30 mmHg, a specific justification must be documented in the subject's source records and on the case report form. Use of an IOP lowering agent under these conditions is not a reason for discontinuing a subject from the study. However, they are to be excluded from the Per Protocol (PP) and Best Case analysis populations.

For any IOP measurement ≥ 30 mmHg at a study visit (or as determined as medically necessary by the Investigator), the Investigator should institute a treatment consisting of one or a combination of the following options:

- Aqueous fluid release through corneal incision;
- Topical eye drops (e.g., *B*-blocker, prostamide, etc.);
- Oral medication (e.g., acetazolamide).

An IOP ≥ 30 mmHg at a study visit must be rechecked in approximately one (1) hour after the initial IOP measurement.

In the event of an IOP \geq 30 mmHg or the use of an IOP lowering treatment, the Investigator should contact the Sponsor and its representative immediately.

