11.1 Schedule of Evaluations and Procedures

Enrolled subjects who meet eligibility criteria will be seen according to the following schedule:

Table 2. Schedule of Evaluations and Procedures

Preoperative Visit	Days -60 to -1
Operative Examination	Day 0
Postoperative Visit 1*	6 Hours \pm 2 hours postoperatively

Postoperative Visit 2	24 Hours \pm 4 hours postoperatively
Postoperative Visit 3	7 Days \pm 2 days postoperatively
Postoperative Visit 4	30 Days \pm 7 days postoperatively
Postoperative Visit 5	90 Days \pm 14 days postoperatively

* Postoperative Visit 1 must occur on the same day as the Operative Visit.

Refer to [Appendix A](#) for the schedule of visits and parameters and [Appendix B](#) for methods of clinical evaluation.

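### Section 9.1.3 takes a subject out of the study when another OVD is used, so the eye stays in ITT but its only postoperative ECD will probably be lost and imputed as for an ordinary eye of its arm

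*Combined protocol and SAP*

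**What the plan says.** Section 9.1.3 bars any other OVD alongside the assigned one and adds: "Use of any other OVD will require immediate discontinuation of a subject from the study". If more than one vial of the assigned OVD is needed, "this will be allowed and the incidence of such events will be reported".

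Section 8.3 lists among possible reasons for withdrawal: "When the requirements of the protocol are not followed". The mandatory discontinuation reasons in section 8.3.4 do not name use of another OVD. That section asks that, before discontinuation, "every effort should be made to contact the subject, schedule a final study visit, and obtain as much follow-up data as possible". It then says: "Discontinued subjects should be followed outside of the study protocol". Subjects discontinued after treatment are not replaced. Section 11.1.3 has all treated subjects seen at five postoperative visits.

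IOP-lowering treatment is handled differently. For intraoperative use, section 9.3.2 says: "Use of an IOP lowering agent under these conditions is not a reason for discontinuing a subject from the study". Section 9.3.4 takes the same line for treatment of IOP below 30 mmHg and adds: "However, they are to be excluded from the Per Protocol (PP) and Best Case analysis populations".

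The ITT Population is all randomized eyes (13.4.1). ECD is measured preoperatively and at Visit 5 only (13.5.2; Appendix A; Appendix B, 3.0). Missing ECD in ITT eyes, including after discontinuation, is imputed by MCMC from investigator, treatment, preoperative value and postoperative value (13.5.2).

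**The concern.** A second OVD can only be used during surgery, after randomization, by staff who know the assignment. A surgeon might reach for one because the assigned OVD is not performing well, and that performance is what the trial compares. If the subject then leaves the study, the primary effectiveness outcome is missing for a reason that may be related to its value. The imputation model would give the eye a value typical of its arm.

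In a non-inferiority trial the direction matters. If such events are commoner on the test OVD and those eyes do worse, replacing their outcomes with typical ones favours the non-inferiority claim. If they are commoner on control, the bias runs against the claim. The loss is also avoidable, because the Day 90 visit is already scheduled and the protocol already keeps subjects in after another kind of treatment departure.

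**Working it through.** **Sequence in the text**

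1. Randomization takes place at the Operative Visit before any OVD is used (11.1.2, Appendix C), so the eye is in ITT.
2. Use of another OVD leads to immediate discontinuation from the study (9.1.3), hence on Day 0.
3. Later follow-up is outside the protocol (8.3.4).
4. The only postoperative ECD is due at 90 ± 14 days, so it is probably not collected.
5. The missing value is imputed from four listed variables, none of which marks the event (13.5.2).

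**The plan's own figures**

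Inputs from 13.3.2: 165 per arm, SD 14.2, margin 5, true difference 0, one-sided 0.05. The noncentral t with 328 degrees of freedom and noncentrality 5/(14.2 × √(2/165)) = 3.198 gives 93.90% power, as stated. Enrollment of 165/0.9 = 183.3, rounded up to 184 per arm, also agrees. This point disputes no stated figure.

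**Size of the possible bias**

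The plan supplies 184 per arm, SD 14.2, margin 5 and one-sided 0.05. The documents give nothing on how often the event occurs, how it splits by arm or how such eyes fare. I therefore assume an extra ECD loss D of 10 to 20 points relative to what the model imputes, and give results per net excess test-arm eye, k. No other dropout is assumed. The truth is taken to include these eyes' actual outcomes, which is the ITT reading.

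- SE of the difference = 14.2 × √(2/184) = 1.480.
- Bias per eye = D/184: 10/184 = 0.054 points; 20/184 = 0.109 points.
- Error at the margin = Φ(−1.645 + k × bias/1.480).

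| Net excess test-arm eyes | D = 10 | D = 20 |
|---|---|---|
| 1 | 5.4% | 5.8% |
| 5 | 7.2% | 10.1% |

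The bias that doubles the error to 10% is (1.645 − 1.282) × 1.480, about 0.54 points. That takes about 5 excess eyes at D = 20 or 10 at D = 10, which is 2.7% to 5.4% of the arm. With five excess control eyes at D = 20, the error falls to Φ(−1.645 − 5 × 0.109/1.480) = 2.2%.

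A simulation that carries out the imputation (20,000 trials, 25 imputations drawn within arm, Rubin's rules) agrees: 5.3% and 6.2% for one eye, 7.1% and 10.0% for five, and 5.0% when two eyes in each arm are affected.

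**The case against.** The strongest reply is that the event may hardly ever occur. Extra vials of the assigned OVD are allowed (9.1.3), the two products are expected to behave alike (13.3.1), and eyes at higher surgical risk are excluded (8.2). One excess eye barely moves the error rate. The plan also has worst-case, tipping-point, complete-case and PP analyses for ECD (13.5.2). All of this stands, and it is why the point is of low severity. The sensitivity analyses, however, do not repair the primary test.

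The benchmark is also a choice. If the target were the effect of a single OVD, the outcomes of eyes exposed to two would not simply count, and the truth would differ. The calculation follows the ITT definition because the primary ECD test uses it.

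A reader might infer four stronger points that the documents do not support:

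- *The Day 90 ECD is certainly lost.* Section 8.3.4 asks for a final visit and as much data as possible without giving a date, and 11.1.3 schedules five visits for every treated subject. Loss is probable on a literal reading, not certain.
- *The IOP endpoint is materially biased too.* Section 11.1 says: "Postoperative Visit 1 must occur on the same day as the Operative Visit". An early IOP is therefore likely to be obtained. Any figure for its complete absence would rest on visit-level IOP values that the documents do not give.
- *The event would go unrecorded.* Deviations must be documented with an explanation (9.4), an exit CRF is required (8.3.3), withdrawals are notified through IRT (8.3.4), and the Day 0 questionnaire asks about difficulty with device use (Appendix C). Section 13.5.5 also tabulates the Safety, ITT and PP Populations by treatment. The remaining gap is narrower: reasons for discontinuation are summarized by investigator and overall, not by arm.
- *Section 9.1.3 flatly contradicts the withdrawal sections.* Section 8.3 foresees withdrawal for not following the protocol. The sections leave the data-collection consequence unclear; they do not exclude one another.

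**Conclusion.** The point holds for ECD, as a cheap improvement of low severity. Read literally, 9.1.3 will probably remove the only postoperative ECD of an eye that remains in the primary analysis, and the imputation model treats that eye as ordinary. Bias requires the event to be related to OVD performance and to differ by arm; neither is known. Under the assumed 10 to 20 points of extra loss, the shift is 0.05 to 0.11 points of the 5-point margin per net excess test-arm eye. It would take about 5 to 10 such eyes to double the nominal error. If the event is rare or balanced, the effect is negligible. No material IOP effect is claimed.

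**What to change.** Reconcile 9.1.3 with 8.3.4, 11.1.3 and 13.4.1. Record use of another OVD as a major deviation, name it in 13.5.7, and exclude the eye from PP and Best Case, as 9.3.2 and 9.3.4 do for IOP-lowering treatment. Section 13.5.7 probably covers the event already under incorrect OVD or disallowed treatment, but does not name it. Scheduled IOP, ECD and adverse event collection should continue, and the observed values should enter the primary analyses. In 13.5.5, report the number of such eyes and the reasons for discontinuation by arm. A dedicated questionnaire item is optional.

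The cost is a change of protocol wording, one line in 13.5.7 and an arm split in a planned table; the visits are already scheduled. The downside is that a few eyes exposed to two OVDs enter the ITT comparison and may slightly dilute a device difference, which the planned PP analysis addresses. The change concerns outcome collection only and takes no view on which OVD may be used in surgery.
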